8. DATA MANAGEMENT

For this study subject data will be entered into an electronic case report form, using an inVentiv Health or GSKCH validated data system.

8.1. Source Documents/ Data

The source documents (e.g. screening telephone script, hospital records, clinical and office charts, memoranda, subjects' diaries or evaluation checklists, pharmacy dispensing records, recorded data from automated instruments, microfiches, photographic negatives, microfilm or magnetic media, x-rays, subject files and records kept at the pharmacy, at the laboratory and at the medico-technical departments involved in the clinical study) which contain the source of data recorded in the eCRF should be specified in the Source Document Designation Form. In some cases the eCRF can be used as a source document.

Each subject will be assigned and identified by a unique Screening Number. Any reference made to an individual subject within the study must be done using the unique Screening Number.

Document Name	207872 Clinical Protocol.doc		
Type	Version	Document Identifier	Effective Date
elido_clinical_doc	5.0; Most-Recent; Effective; CURRENT	090032d580d488e0	30-May-2017 04:37:09
Reason For Issue	Auto Issue		

8.2. Electronic Case Report Form

A CRF is a printed, optical, or electronic document designed to record all of the protocol required information to be reported to the sponsor on each trial subject.

For each subject who has given informed consent/assent and has been screened, eCRF must be completed and signed by the Principal Investigator (or authorised designee) to certify that the data are complete and correct.

Management of clinical data will be performed in accordance with applicable GSKCH standards and data cleaning procedures to ensure the integrity of the data e.g. removing errors and inconsistencies in the data.

In order to protect the privacy of subjects, no Personally Identifiable Information (PII) (including the subject's name or initials or birth date) is to be recorded in the eCRF or as part of the query text.

Adverse events and concomitant medications terms (if applicable) will be coded using MedDRA (Medical Dictionary for Regulatory Activities) and an internal validated medication dictionary, GSKDrug.

Subject data will be entered into GSKCH defined eCRFs and transmitted electronically to GSKCH in a validated (21 CFR Part 11 compliant) web-based electronic data capture system.

All eCRF pages should be completed during a subject assessment when the eCRF has been designated as the source. Data that is sourced elsewhere should be entered into the eCRF in an agreed upon timeframe between the Investigator and Sponsor.

At the conclusion of the study, the occurrence of any protocol deviations will be determined. After these actions have been completed and the database has been declared to be complete and accurate, it will be locked and made available for data analysis. Any changes to the database after that time can only be made by joint written agreement between the GSKCH Principal Clinical Research Scientist, the Project Statistician and the Project Data Manager with the authorization from Head of Clinical Research.

Throughout the duration of the study, eCRFs (including queries, query responses and audit trails) will be retained by inVentiv Health. Following decommissioning of the study site data archived compact discs (CD(s)) prepared by inVentiv Health will be sent to the investigator and GSKCH.

Document Name	207872 Clinical Protocol.doc		
Type	Version	Document Identifier	Effective Date
eldo_clinical_doc	5.0; Most-Recent; Effective; CURRENT	090032d580d488e0	30-May-2017 04:37:09
Reason For Issue	Auto Issue		

8.3. Data Handling

Documentation of all data management activities should allow step-by-step retrospective assessment of data quality and study performance. Any changes or corrections to data will be performed in the Electronic Data Capture (EDC) System, and it will include rationale for changes. The EDC system has an audit trail, which will provide a complete record of the changes and corrections endorsed by the Investigator.

8.3.1. Data Queries

Programmed edit checks will be generated automatically, as the data is being entered into the system. Data Management will also run reports and listings on the eCRF data, in addition to the queries already programmed and generated by the system, to raise manual queries as needed for site clarification or correction. The Clinical Dictionary Development and Management Group will raise queries as needed on safety data to code the terms (Adverse Events and Drugs) are reported appropriately.

The study monitor at the clinical site will review the eCRFs in accordance with the monitoring plan, and any queries will be generated in the EDC System to the Investigator or designee, enabling the errors to be addressed in parallel with Data Management review. The study monitor can also run reports and listings on the eCRFs, to raise manual queries as needed for site clarification or correction

8.4. Processing Patient Reported Outcomes

Patient reported outcome (PRO) data are collected directly from the subject PRO measures e.g. diary cards, questionnaires etc, and entered into the sponsor's clinical data management system (DMS) by the study site representative. PRO's that are source will be retained by the investigator and certified copies will be sent to GSKCH.

In order to protect the privacy of subjects, no Personally Identifiable Information (PII) (including the subject's name or initials or birth date) is to be recorded on all PRO's that will be forwarded to GSKCH.

9. STATISTICAL CONSIDERATIONS AND DATA ANALYSES

All statistical activities will be conducted by inVentiv Health under the guidance of GSKCH.

Document Name	207872 Clinical Protocol.doc		
Type	Version	Document Identifier	Effective Date
elido_clinical_doc	5.0; Most-Recent; Effective; CURRENT	090032d580d488e0	30-May-2017 04:37:09
Reason For Issue	Auto Issue		

9.1 Sample Size Determination

A sufficient number of subjects will be screened to randomise at least 220 subjects to ensure 200 evaluable subjects complete the study. This will ensure approximately 50 evaluable subjects per treatment arm.

This study has not been formally powered to make any claims, and is appropriately sized as a PoP study for the purpose of observing meaningful trends.

9.2. General Considerations

9.2.1. Definition of Analysis Populations

The All Subjects population includes all subjects who enter the study and sign the informed consent form. This population includes screen failures as well as those that are randomised.

The Safety population will include all subjects who are randomised and receive at least one dose of investigational product and will be reported by treatment received.

The Intent-To-Treat (ITT) population will include all subjects who are randomised, receive at least one dose of investigational product and have at least one post-baseline efficacy evaluation and will be reported by randomised treatment.

The Per Protocol (PP) population will include all subjects in the ITT population who have at least one efficacy assessment considered unaffected by protocol violations. Efficacy assessments considered affected by protocol violations will be excluded from PP analysis.

Repeatability subjects are those subjects that have an initial and a repeat stain assessment.

The primary population for assessment of efficacy will be the ITT population. A PP analysis will be performed on the primary variable only if more than 20% of the subjects in the ITT population are excluded from the PP population.

The Safety population will be used for all safety and tolerability reporting.

9.2.2. Exclusion of Data from Analysis

The following will be considered as major protocol deviations leading to the exclusion of subjects / data for PP analysis:

Document Name	207872 Clinical Protocol.doc		
Type	Version	Document Identifier	Effective Date
elido_clinical_doc	5.0; Most-Recent; Effective; CURRENT	090032d580d488e0	30-May-2017 04:37:09
Reason For Issue	Auto Issue		

- Deviation from the inclusion/exclusion criteria likely to affect efficacy.
- The use of prohibited medication likely to affect efficacy.
- Not receiving randomised treatment

Other deviations likely to result in exclusion from the PP population will be detailed in the statistical analysis plan (SAP).

Protocol violations deemed to affect efficacy will be identified between the Biostatistician and Clinical Research Director or designee, ahead of breaking the study blind.

9.2.3. Criteria for Evaluation

Efficacy will be evaluated by the ITT or PP population. Safety will be assessed by the safety population.

9.2.4. Criteria for Assessing Efficacy

Efficacy will be evaluated based on the ranking performance of the study treatments on the stain variables. The minimum requirement will be similar, or lower levels of stain for at least one of the experimental products compared to the standard fluoride dentifrice (Colgate Cavity Protection®). The marketed SnF₂ dentifrice (Sensodyne Complete Protection) will be expected to demonstrate a comparable, or statistically significantly better performance on the stain parameters versus the experimental products and Colgate Cavity Protection®.

9.2.5. Criteria for Assessing Tolerability

The safety profile of the study treatments will be assessed with respect to adverse events (AEs) and oral soft tissue (OST) abnormalities.

9.2.6. Handling of Dropouts and Missing Data

Subjects who withdraw from the study early will be included in the statistical analysis up to the time point when they withdraw. Missing data will not be replaced.

Document Name	207872 Clinical Protocol.doc		
Type	Version	Document Identifier	Effective Date
elido_clinical_doc	5.0; Most-Recent; Effective; CURRENT	090032d580d488e0	30-May-2017 04:37:09
Reason For Issue	Auto Issue		

9.3. Statistical Methods and Analytical Plan

Additional details of the proposed statistical analysis will be documented in the statistical analysis plan (SAP), which will be written following finalisation of the protocol and prior to study unblinding.

9.3.1. Demographic and Baseline Characteristics

Descriptive statistics (number of subjects, mean, standard deviation, median, minimum and maximum for continuous variable, and frequency and percentage for categorical variables) will be provided for demographic and baseline data.

9.3.2. Primary Analysis

The primary variable will be overall MLSI at Week 4. This variable will be analysed using analysis of covariance (ANCOVA) with treatment and smoking status as factor, and pre-prophylaxis baseline mean MLSI score as the covariate. Adjusted means and treatment differences between the two test products and the marketed standard fluoride dentifrice, and the treatment difference between the marketed SnF₂ dentifrice and the marketed standard fluoride dentifrice will be provided together with their 95% CIs and p-values.

The assumption of residual normality in ANCOVA analysis will be investigated. If violated, data transformation or a non-parametric method (e.g., the Wilcoxon rank sum test) will be applied.

9.3.3. Secondary Analysis

The secondary variables will be overall MLSI (A×I) at Week 4 for the treatment differences between the two test products and the marketed SnF₂ dentifrice, and the treatment difference between the marketed SnF₂ dentifrice and the marketed standard fluoride dentifrice.

These will be analysed and results summarised in the same way as per the primary variable but with the appropriate baseline term as the covariate.

9.3.4. Exploratory Analyses

Exploratory variables include overall MLSI Intensity score at Week 2, and Interproximal MLSI score, overall MLSI Area score and overall MLSI Intensity score at Weeks 2 and 4. Each of these variables will be analysed using the same ANCOVA

Document Name	207872 Clinical Protocol.doc		
Type	Version	Document Identifier	Effective Date
elido_clinical_doc	5.0; Most-Recent; Effective; CURRENT	090032d580d488e0	30-May-2017 04:37:09
Reason For Issue	Auto Issue		

model as in the primary analysis with the appropriate baseline term as the covariate. Adjusted means of all treatments and treatment differences will be provided together with their 95% CIs and p-values.

9.3.5. Safety Analyses

For the assessment of safety and tolerability, treatment emergent AEs will be summarised by treatment group. AEs and incidents will be listed. No inferential analyses will be performed to compare treatments with respect to safety data.

The safety profile of the study treatments will be assessed with respect to AEs. OST abnormalities are included as AEs if they appear or worsen after the initial assessment.

All safety data will be reported for the Safety population as per actual treatment received. All subjects screened will be included in the list of AEs.

All AEs will be reviewed by the Clinical Research Director or Designee prior to database freeze and will be coded using the Medical Dictionary for Regulatory Activities (MedDRA). During this review stage, AEs will be further categorised as oral or non-oral.

AEs will be regarded as treatment emergent if they occur on or after the start date and time of the first treatment usage (as determined by start date and time from the EXPOSURE/dispensing panel; if this date is missing a suitable alternative will be used eg date and time of randomisation). All other AEs prior to this will be considered non-treatment emergent.

The following summary tables and listings will be presented by treatment group.

- Table of treatment emergent AEs by Oral/Non-Oral and Preferred Term
- Table of treatment emergent AEs by SOC and Preferred Term
- Table of Treatment emergent treatment related AEs by Oral/Non-Oral and Preferred Term
- Table of treatment emergent treatment related AEs by SOC and Preferred Term
- Listing of all AEs (including Non-treatment emergent from All Subjects)
- Listing of SAEs
- Listing of incidents

In the event that there is nothing to report a null listing will be produced.

Document Name	207872 Clinical Protocol.doc		
Type	Version	Document Identifier	Effective Date
elido_clinical_doc	5.0; Most-Recent; Effective; CURRENT	090032d580d488e0	30-May-2017 04:37:09
Reason For Issue	Auto Issue		

No inferential analyses will be performed to compare treatments with respect to safety.

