Procedure	Pre-screening	Visit 1 Screening		Visit 2 Baseline Day 0	Visit 3 Week 2 Day 14 ± 2 days	Visit 4 Week 4 Day 28 ± 2 days
Telephone Screening of Subjects	✓					
Informed Consent		✓				
Demographics, Medical History, Smoking Status		✓				
Current / Concomitant Medication		✓		✓	✓	✓
Oral Soft Tissue (OST) Examination		✓		✓		
Full Oral Hard Tissue (OHT) Examination		✓		✓		
Visual MLSI Stain Assessment		✓				
Inclusion / Exclusion Criteria		✓		✓		
Eligibility		✓		✓		
Brush Anterior Teeth for 30 Seconds with Tap Water Prior to Stain Assessment				✓	✓	✓
Pre-prophylaxis Full MLSI Stain Assessment of the Anterior Teeth ¹				✓		
Stratification / Randomisation				✓		
Dental Prophylaxis ²				✓		
Post-prophylaxis Visual MLSI Stain Assessment				✓		
Full MLSI Stain Assessment ¹					✓	✓
Dispense Study Dentifrice, Timer, Toothbrush and Diary/Instructions Card				✓		
Supervised Brushing on Site				✓ ³	✓	
Adverse Events				✓	✓	✓
Incidents				✓ ⁴	✓	✓
Subject Adherence and Continuance					✓	✓
Diary Compliance Check ⁵					✓	✓
Return Dentifrice, Toothbrush and Diary Card					✓	✓
Post Treatment Dental Prophylaxis						✓ ⁶
Study End						✓

Minimum 24 hours, up to a maximum of 2 weeks

1. Ten subjects will be randomly selected for repeat examinations across each assessment window (a total of 30 repeat examinations over the duration of the study).
2. AEs will be recorded from and including dental prophylaxis onwards.
3. Time of first brushing will be captured to distinguish dentifrice AEs from prophylaxis AEs.
4. Incidents will be collected from first use of the tooth brush, prior to stain assessment.
5. Time of each brushing occasion in addition to missed/additional brushings, and changes to smoking status will be captured in the subject diary.
6. Once all efficacy assessments have been completed randomised subjects who request so will be given a full dental prophylaxis, and will be recorded in the eCRF.

Document Name	207872 Clinical Protocol.doc		
Type	Version	Document Identifier	Effective Date
elido_clinical_doc	5.0; Most-Recent; Effective; CURRENT	090032d580d488e0	30-May-2017 04:37:09
Reason For Issue	Auto Issue		

PROTOCOL SYNOPSIS FOR STUDY 207872

Brief Summary

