7. SAFETY ASSESSMENTS

7.1. Definitions of an Adverse Event and Serious Adverse Event

7.1.1. Adverse Events

The investigator or site staff will be responsible for detecting, documenting and reporting events that meet the definition of an AE or SAE.

Adverse Event Definition:

- An AE is any untoward medical occurrence in a patient or clinical investigation subject, temporally associated with the use of an investigational product or clinical procedure, whether or not considered related to the investigational product or clinical procedure (eg. dental prophylaxis).
- NOTE: An AE can therefore be any unfavorable and unintended sign (including an abnormal laboratory finding), symptom, or disease (new or exacerbated) temporally associated with the use of an investigational or clinical procedure (eg. dental prophylaxis).

Events meeting AE definition include:

- Any abnormal laboratory test results (if applicable) or other safety assessments, including those that worsen from baseline, and felt to be clinically significant in the medical and scientific judgment of the investigator.
- Exacerbation of a chronic or intermittent pre-existing condition including either an increase in frequency and/or intensity of the condition.
- New condition(s) detected or diagnosed after study product administration even though it may have been present prior to the start of the study.
- Signs, symptoms, or the clinical sequelae of a suspected interaction.
- Signs, symptoms, or the clinical sequelae of a suspected overdose of either study product or a concomitant medication (overdose per se will not be reported as an AE/SAE).

Events NOT meeting definition of an AE include:

- Any clinically significant abnormal laboratory findings (if applicable) or other abnormal safety assessments which are associated with the underlying disease, unless judged by the investigator to be more severe than expected for the subject's condition.

Document Name	207872 Clinical Protocol.doc		
Type	Version	Document Identifier	Effective Date
elido_clinical_doc	5.0; Most-Recent; Effective; CURRENT	090032d580d488e0	30-May-2017 04:37:09
Reason For Issue	Auto Issue		

- The disease/disorder/ condition being studied or expected progression, signs, or symptoms of the disease/disorder being studied, unless more severe than expected for the subject's condition..
- Medical or surgical procedure (e.g., endoscopy, appendectomy): the condition that leads to the procedure is an AE.

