7.2. Recording Adverse Events and Serious Adverse Events

Recording of adverse events and serious adverse events:

- The investigator or site staff will be responsible for detecting, documenting and reporting events that meet the definition of an AE or SAE.
- The investigator or site staff will then record all relevant information regarding an AE/SAE in the eCRF.
- There may be instances when copies of medical records for certain cases are requested by GSK. In this instance, all subject identifiers, with the exception of the subject number, will be blinded on the copies of the medical records prior to submission to GSK.
- The investigator will attempt to establish a diagnosis of the event based on signs, symptoms, and/or other clinical information. In such cases, the diagnosis will be documented as the AE/SAE and not the individual signs/symptoms. Clinical AEs will be described by diagnosis and not by symptoms when possible (e.g., upper respiratory tract infection, seasonal allergy, etc. instead of runny nose).
- AEs will be collected from dental prophylaxis and until 5 days following last administration of the study product.
- SAEs will be collected over the same time period as stated above for AEs. However, any SAEs assessed as related to study participation (e.g., investigational product, protocol mandated procedures, invasive tests, or change in existing therapy) or related to a GSK concomitant medication will be recorded from the time a subject consents to participate in the study up to and including any follow-up contact.
- Medical conditions reported prior to the time period for reporting AEs/SAEs should be recorded as part of the subject's medical history.

Document Name	207872 Clinical Protocol.doc		
Type	Version	Document Identifier	Effective Date
elido_clinical_doc	5.0; Most-Recent; Effective; CURRENT	090032d580d488e0	30-May-2017 04:37:09
Reason For Issue	Auto Issue		

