4.7 Analysis of Safety

4.7.1 Adverse Events and Serious Adverse Events

All safety data will be reported for the Safety population as per actual treatment received. All subjects screened will be included in the list of AEs.

AE will be regarded as treatment emergent if they occur on or after the start date and time of the first treatment usage (as determined by start date and time from the EXPOSURE/dispensing panel; if this date is missing a suitable alternative will be used eg date and time of randomisation). All other AEs prior to this will be considered non-treatment emergent.

All AEs will be reviewed by Clinical Research prior to database freeze and will be coded using the Medical Dictionary for Regulatory Activities (MedDRA). During this review stage, AEs will be further categorized as oral or non-oral.

The following summary tables and listings will be presented by treatment group.

- Table of treatment emergent AEs by Oral/Non-Oral and Preferred Term ([Table 14.3.1.2](#))

- Table of treatment emergent AEs by SOC and Preferred Term ([Table 14.3.1.1](#))
- Table of treatment emergent AEs by SOC, Preferred Term and Severity ([Table 14.3.1.3](#))
- Table of Treatment emergent treatment related AEs by Oral/Non-Oral and Preferred Term ([Table 14.3.1.4](#))
- Listing of all AEs (including all subjects: Listing 16.2.7.1 for all randomised subjects; Listing 16.2.7.2 for non-randomised subjects)
- Listing of death ([Listing 14.3.2.1](#))
- Listing of non-fatal SAEs ([Listing 14.3.2.2](#))
- Listing of treatment emergent AEs leading to withdrawal ([Listing 14.3.2.3](#))
- Listing of treatment emergent AEs classified as oral ([Listing 14.3.2.4](#))

In the event that there is nothing to report a null listing will be produced.

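### The treatment-emergent rule has no worsening criterion, so a prophylaxis-onset AE that worsens under the dentifrice can be left out of the treatment-emergent outputs, depending on how the site records it

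*Protocol*

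**What the plan says.** **The rule.** Protocol 9.3.5: "AEs will be regarded as treatment emergent if they occur on or after the start date and time of the first treatment usage". SAP 4.7.1 has the same wording: "AE will be regarded as treatment emergent if they occur on or after the start date and time of the first treatment usage". It then closes off the alternative: "All other AEs prior to this will be considered non-treatment emergent". The protocol closes it off in the same way. If the first-use date is missing, Protocol 9.3.5 adds: "if this date is missing a suitable alternative will be used eg date and time of randomisation".

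**When AEs are collected.** Protocol 7.2: "AEs will be collected from dental prophylaxis and until 5 days following last administration of the study product". Footnote 3 to the protocol's Schedule of Events explains why the first brushing is timed: "Time of first brushing will be captured to distinguish dentifrice AEs from prophylaxis AEs".

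**Worsening as an AE.** Protocol 7.1.1 lists among events that are AEs: "Exacerbation of a chronic or intermittent pre-existing condition including either an increase in frequency and/or intensity of the condition". The note to the AE definition in the same section is broader. It covers signs, symptoms or disease that are aggravated as well as those that are new. Protocol 9.3.5 also counts OST abnormalities as AEs if they get worse after the first examination.

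**Outputs.** Every AE table in Protocol 9.3.5 and SAP 4.7.1 is limited to treatment-emergent events. So are two SAP listings: oral AEs (14.3.2.4) and "Listing of treatment emergent AEs leading to withdrawal" (14.3.2.3).

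**The concern.** The design gives every randomised subject who has the prophylaxis a short period in which an AE can be recorded before the dentifrice is used. The plan sorts events into prophylaxis AEs and dentifrice AEs by time alone. An event that starts at the prophylaxis and is then aggravated by the dentifrice belongs to both, and the rule has no place for it.

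Take soreness that begins during the cleaning, is recorded as mild, and becomes severe after several days of brushing. If it remains one record, its onset precedes first use and it is non-treatment emergent, whatever happens later. The events at issue would be mostly oral, and Protocol 9.2.5 judges tolerability on AEs and OST abnormalities. Safety is reported descriptively, so the treatment-emergent tables carry most of the tolerability message. A subject could be counted as an adverse-event discontinuation in the disposition table and yet be missing from the SAP listing of AEs leading to withdrawal.

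**Working it through.** The plan gives no figure to reproduce. The check is to apply the written rule to the order of events at Visit 2.

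**Order at Visit 2** (Protocol 3.1): randomisation, prophylaxis, visual stain check, dispensing, first supervised brushing. AE collection opens at the prophylaxis (Protocol 7.2; Schedule of Events, footnote 2). The interval at issue runs from the prophylaxis to the first brushing, within one visit.

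**An AE that starts in that interval and worsens after first brushing**

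| How it is recorded | Classification under the written rule | Where it appears |
|---|---|---|
| (a) One record, original onset kept | Non-treatment emergent | All-AE listing; SAE or death listing if serious; disposition table if it leads to discontinuation. Absent from the treatment-emergent tables and from Listings 14.3.2.3 and 14.3.2.4 |
| (b) Worsening entered as a separate AE dated at the worsening | Treatment emergent | All relevant tables and listings |
| (c) First-use date missing, randomisation used instead | Treatment emergent, because randomisation precedes the prophylaxis | All relevant tables and listings |

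So the exclusion occurs in (a) and not in (b) or (c). Case (c) is no remedy: it arises only when a date is missing, and it would also make pure prophylaxis events treatment emergent.

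**Do the documents choose between (a) and (b)?**

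- For (b): the note in Protocol 7.1.1 and the OST sentence in 9.3.5 allow a worsening to be an AE in its own right.
- For (a): the specific example in 7.1.1 is confined to chronic or intermittent conditions, which acute soreness does not clearly fit. Protocol 7.2 asks for a diagnosis rather than separate symptoms, 7.3 assigns an intensity to each AE, and 7.5 follows each AE to resolution. Together these point towards one continuing record.
- Scheduled OST examinations take place at Visits 1 and 2 only (Protocol 6.1.5), so none follows home use.
- No section tells the site to open a new record when an existing AE gets worse.

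The choice is therefore left to the site.

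**Size of one event.** At least 220 subjects are to be randomised to four arms (Protocol 9.1). Assuming equal arms, 220/4 = 55 per arm, and one event is 1/55 = 1.8% of an arm. The documents give no AE rates, so the number of such events cannot be derived.

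**The case against.** The strongest reply is that the protocol already provides a route. The note in 7.1.1 is not limited to chronic conditions. Under Protocol 6.1.5 an abnormality reported by the subject after dentifrice use is recorded as an AE, so no scheduled examination is needed. A worsening recorded that way falls after first use and is treatment emergent under the existing rule. This stands as far as it goes: the route is permitted, but it is not required.

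The interval is also short. Any soreness that starts after the first brushing is already treatment emergent, even if the prophylaxis caused it. This stands too, and it limits the size of the problem.

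Three stronger readings are tempting, and the documents do not support them:

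- *Such an event is always left out of the treatment-emergent outputs.* This follows only if the site keeps a single record.
- *The event, or its worsening, is lost.* Listing 16.2.7.1 is set out by treatment group and is not restricted to treatment-emergent events. It marks oral AEs and has columns for relatedness, action taken, outcome, seriousness and withdrawal. Table 14.1.1 counts adverse-event discontinuations by arm. The listing shell has one onset and one intensity field per event, but a shell does not rule out a second row, and the eCRF is not among the documents. Nor do they say whether the recorded intensity is the initial or the worst.
- *A count of missed events can be given.* Suppose 5% to 15% of subjects have an oral AE starting at the prophylaxis and 10% to 30% of those worsen. Then 55 × 0.05 × 0.10 = 0.3 to 55 × 0.15 × 0.30 = 2.5 events per arm. Both rates are guesses, and the product assumes that every worsening stays on the old record. It is not an estimate.

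Finally, this is a proof-of-principle study with no inferential safety comparison, and no efficacy result is touched. That limits the weight of the point but does not make the classification clear.

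**Conclusion.** The point holds in conditional form. The treatment-emergent rule has no worsening criterion in either document, and AE collection begins before first dentifrice use. A prophylaxis-onset AE that later worsens is misclassified if it is kept as one record, and correctly classified if the worsening is entered separately. Two members of staff could therefore classify the same event differently without either breaching the protocol.

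The effect is confined to the treatment-emergent tables and the two restricted SAP listings. The number of events is unknown and probably small, because the interval lies within a single visit. The 1.8% per event rests on the minimum planned enrolment and equal arms. The conclusion rests on the rule as written and on the absence of a recording instruction in the documents; an eCRF completion guide that supplied one would largely answer it.

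**What to change.** In Protocol 9.3.5 and SAP 4.7.1, define an AE as treatment emergent if either of these applies:

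- it starts on or after first use of study dentifrice; or
- it started earlier, including at the prophylaxis, and increases in intensity or becomes serious on or after first use.

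Instruct the site, in the protocol or the eCRF completion guide, to enter such worsening as a new AE record with its own start date, time, intensity and causality.

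The cost is one sentence in each document and one completion instruction. No new visits or data items are needed. The downside is a slightly higher treatment-emergent count.
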